7.3.2 Physical Health

Possible atrial fibrillation detected during Heartbeat Detection Task: If possible atrial fibrillation is indicated by the Kardia Mobile device during the “Heart Beat Detection Task” a safety flag will appear notifying the research assistant (RA) administering the assessment. The RA will then implement the MB-BP safety protocol.

Out-of-range blood pressure readings: If during an in-person assessment the participants systolic blood pressure (SBP) and/or diastolic blood pressure (DBP) falls outside of the acceptable range outlined in the safety protocol, the RA will be notified and the IRB approved safety protocol will be implemented.

Injury due to physical activities: It is possible that injuries could be sustained from (1) the gentle mindful movements (yoga), or (2) physical activities that participants engage in as a result of the intervention encouraging exploration of physical activity as a way to reduce blood pressure.

- (1) Mindful movements: Participants receive a handout during the orientation showing the yoga poses that will be offered during the course. They are encouraged to explore limits in their body related to movement, but not to go beyond those limits. Participants are asked to listen to what their body is telling them more closely than what the mindful movement instructor is telling them. Modifications of poses are available, including for those limited to chairs or wheelchairs. Participants are encouraged to bring the handout of poses to their health care providers if they have any physical limitations, so that the providers can advise on which poses to do, and which to avoid.
- (2) Physical activities: Participants are encouraged to explore physical activities that promote strength and conditioning as a way to reduce blood pressure. As with the mindful movements, they are encouraged to explore limits in their body related to movement, but not to go beyond those limits. Participants are asked to listen to what their body is telling them more closely than what the mindful movement instructor is telling them. Furthermore, they are encouraged to ask their healthcare provider about advised physical activities if they have any physical limitations.

Note that adverse events related to physical injuries will be captured during the routine safety check-ins (discussed above).

7.3.3 Other

Participant Initiated (Passive monitoring): Participants are encouraged to contact meditation instructors and/or study staff if any physical or mental health symptoms arise or other study or meditation-related problems occur. Participants may report AEs at any time throughout the study. Events will be evaluated with the Adverse Events Form by study staff.

Attrition: Reasons for attrition are also an important source of AEs, but are rarely assessed adequately, as participants are unlikely to give honest answers if queried directly by study staff. To increase the accuracy of attrition reason reporting, participants will be asked to complete a brief online Participant-initiated dropout reason survey (see Appendix A7).

Investigator-initiated withdrawals: In rare circumstances, a study participant may be withdrawn from the study and/or intervention by the researcher. In this case, the researcher or other study staff should complete the Attrition information form, and describe reasons for attrition. Note, however, that this scenario would be very unusual, and has not happened once in the in the approximately 130 participants who have gone through the MP-BP study to date. Potential reasons for investigator-initiated withdrawal would be MB-BP classroom or assessment disruption in ways that are causing harm or an unsafe environment for other classroom participants, the instructor, or study staff. The screening questionnaire excludes participants with mental health criteria that puts them at higher risk for disruption. We expect this scenario to occur extremely rarely (as evidenced to date), but remains a possibility.

fMRI Study Safety Monitoring: it is possible participants may experience or report an AE or SAE during their involvement with the fMRI Study. Research staff will use the Adverse Events Form and accompanying documents found in the Appendices to document all AE/SAE discovered at the time of involvement in the fMRI imaging study. The logged events will then be communicated to the Coordinating Center, so that they can be included in the participant file as well as in the annual Data and Safety Monitoring Reports presented to the DSMB. Reporting procedures for AEs and SAEs related to the study will be followed including reporting all SAEs to the study PI and DSMB committee chair.

Non-Response to Treatment: The possibility that the treatment will not yield benefit is another possible risk and will be explained during informed consent procedures. Non-responders (identified as minimal change in medical regimen adherence from baseline assessment) will be provided with referrals to other treatment, if desired.

The data collection systems we have set up to monitor and record AEs and SAEs are specifically designed to avoid double capture. Unique participant identifiers, dates and details surrounding events, as well as steps taken to follow up are recorded.

7.4 Safety Monitoring

Oversight of internal monitoring of the participants' safety will be conducted by the local PI, [name]. Oversight of the external Data and Safety Monitoring Committee will be conducted by the chair ([name]). The Data and Safety Monitoring Committee will include experts in cardiology ([name]), psychology/psychiatry ([name]), epidemiology ([name]), and biostatistics ([name]).

Entities Conducting Monitoring: The Institutional Review Board (IRBs) at Brown University will review all research procedures, and will provide oversight. Internal monitoring will be done by the Brown University principal investigator ([name]) and the Brown University IRB. The Data Safety Monitoring Committee will provide external monitoring, and will meet annually by phone, video conference, or in-person. They will be provided data annually in order to evaluate potential effects of the RCT on major outcomes (e.g. medical regimen adherence). Any serious adverse effects will be immediately reported to the principal investigator ([name]) and the committee chair.

What is Monitored: Monitoring is done of all procedures to ensure that they conform to the approved protocol; of unforeseen circumstances that might arise and affect safety; of all reports of serious adverse events as defined in US Department of Health and Human Services regulations for the protection of human research subjects 45 CFR Part 46, and the FDA 312.32 (death, life-threatening experience, new or prolonged hospitalization, persistent or significant disability/incapacity); of other significant adverse events (adverse events that lead to drop out by participant or termination by the investigator); of unexpected adverse events resulting from the study; and of expected adverse events.

Monitoring is done of all study inclusion and exclusion criteria. During this clinical trial, we will notify officials, as mandated by law, if a participant reports intention to harm him/herself or others, or reports child abuse or abuse of an elder. [name], a licensed psychiatrist, will be available to advise on any psychological events that occur, and provide referrals for treatment if needed.

Frequency of Monitoring: All adverse events will be continuously monitored by the PI as they are documented by the study staff in accordance with the protocol (Please see section 7.3). Participants will be given contact information so that they can inform us of events that occur in between study visits. The PI will meet with staff weekly as schedules allow to review participant progress and to check in about the experiences with the experimental procedures, including adverse events. Any adverse events that are observed and/or reported will be reported to [name] and the Data Safety Monitoring Committee chair under the proposed timelines in the DSMP. The Investigators and DSMB members will be available to meet outside of the regularly scheduled meetings (scheduled annually), if necessary, due to concerns regarding a particular participant or any problems that may arise for participants. If necessary, they will make appropriate recommendations for changes in protocol, or terminate the study. The Brown University IRB conducts the monitoring at the continuing reviews as scheduled, whenever modification requests are considered, and upon receiving reports of serious adverse events from the PI or anyone else.

Reporting Plan: Any serious adverse events that are observed and/or reported will be immediately reported to [name] and the Data Safety Monitoring Committee Chair. Serious adverse events related to the study are then reported to the Brown University IRB and to NIH. Brown University's IRB requires fatalities related to the study be reported within 24 hours. All serious adverse events related to this study will be reported to the Brown University IRB immediately by telephone and by written report within 48 hours of our receipt of information regarding the event. All other adverse events related to the study will be reported at the continuing review. Serious adverse events related to the study will also be reported in writing to the NIH Project Officer within 48 hours of the PI becoming aware. All serious adverse events related to the study will be reported annually in the Progress Report sent to the NIH Project Officer. Data on all AEs and SAEs will be recorded.

Any actions taken by the IRB, other than acceptance of the adverse event report, will be reported to the NIH along with any changes or amendments to the protocol requested by the IRB in response to these reports. Proposed changes or amendments to the protocol in general must be approved in writing by both the Brown University IRB as well as by the funding agency, NCCIH.

8. INTERVENTION DISCONTINUATION

This study will be stopped prior to its completion if: (1) the intervention is associated with adverse effects that call into question the safety of the intervention; (2) difficulty in study recruitment or retention will significantly impact the ability to evaluate the study endpoints; (3) any new information becomes available during the trial that necessitates stopping the trial.

9. STATISTICAL CONSIDERATIONS

9.1 General Design

Analyses will evaluate (1) whether MB-BP influences self-regulation targets, (2) whether the MB-BP-induced changes in self-regulation targets are associated with changes in medical regimen adherence, and (3) whether MB-BP is associated with medical regimen adherence. Analyses will incorporate generalized linear models (GLM) with properly chosen link functions, performed using generalized estimating equations (GEE) with robust standard error estimators.^{245,246} This provides an extension of regression analysis to the case of correlated or repeated observations, allows for inclusion of both continuous and discrete dependent variables, and enables modeling of covariance structures when observations are correlated across time. Following “intention-to-treat” principles, analyses will be conducted on all participants in the randomized controlled trial, regardless of intervention completion. Analyses will use GLM with identity links for normally distributed data. The between-groups independent variable in the GEE analysis is intervention condition, with control conditions as distinct referent groups. Categorical variables will be included in GLM/GEE models as indicator variables with one level chosen as referent. Continuous independent variables such as age and baseline blood pressure would be included as linear terms. In addition, we will include assessment time as a linear term and possibly with an additional quadratic term to capture possible non-linear relationship of time with the outcomes. It is conceivable that one would observe a steeper slope in the initial months that would decrease in the pursuing months. Thus, the use of a quadratic term for assessment time would be able to capture these phenomena. To evaluate self-regulation targets as mediators of the effects of MB-BP on medical regimen adherence, mediation analyses described by Valeri and VanderWeele will be employed.²⁴⁷ Such analyses will allow for potential interactions between the exposure and mediator of interest and account for potential confounders of the exposure-mediator, mediator-outcome, and exposure-outcome relationships using standard regression techniques. These methods estimate total, indirect and direct effect sizes, as well as statistical variance.²⁴⁷

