Study enrollment will continue until target enrollment goals are reached (i.e., n=50 for MBBP intervention group and n=50 for enhanced usual care control group).

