9.2 Sample Size and Randomization

Treatment Assignment Procedures

Statistical Power:

Utilizing effect sizes and statistical variance from the Stage 1 MB-BP clinical trial showed an increase of MAIA from baseline of mean 22.6 (SD=6.5) to mean 26.3 (SD=6.0) at 6-month follow-up, demonstrating a 3.7 increase in MAIA score ($p < 0.001$). Power analyses using the T statistic and non-centrality parameter, with alpha (two-tailed) set at 0.05 and beta at 0.2, shows with a MAIA increase of 3.7 in MB-BP vs. control, sample size requirements are 46 per group. With DASH diet score increasing from 2.78 (SD=0.61) at baseline to 3.37 (SD=0.81) at 6-month follow-up in the Stage 1 MB-BP study in the 67% of participants with a low DASH score (< 5.5), demonstrating a DASH diet score increase of 0.59 ($p < 0.001$). Using an effect size of 0.5, power analyses using the T statistic and non-centrality parameter

suggest that, with alpha (two-tailed) set at 0.05 and beta at 0.2, a sample size of 33 per group will be sufficient.

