Using simulations from Fritz and MacKinnon,²⁴⁸ for 80% power to detect a mediated effect when effect of exposure on mediator, and mediator on outcome, is of small to medium strength (standardized Cohen's d effect sizes of 0.26-0.39 each), based on Sobel first-order test, we will need 90 participants. Given that 67% of Stage 1 participants had DASH diet score <5.5, recruiting a sample size of 160 participants across the UH2 and UH3 phases (Figure 1), this would allow for 107 participants with low DASH diet to be included in primary mediation analyses with DASH diet score as the outcome. Stage 1 effect sizes on DASH diet score were large Cohen's d (d=0.82). Effect sizes on the primary self-regulation outcome was medium (MAIA Cohen's d=0.59). Assuming associations between the MAIA and DASH diet score are in the small to medium range, the study should be adequately powered for mediation analyses. Please note that Stage 1 analyses also demonstrated significant improvements in other health behaviors, including alcohol consumption and physical activity following the MB-BP intervention. Secondary analyses will evaluate impacts of MB-BP on these health behaviors, but are not adequately powered for mediation analyses due to the lower proportion of participants that do not adhere to these behavioral AHA guidelines (i.e. approximately 15% of participants do not comply to AHA alcohol guidelines, and 32% do not adhere to physical activity guidelines in our Stage 1 sample).

The fMRI imaging analyses (n=24 per group) should be adequately powered, based on power calculations shown in the MINDFUL-PC study below and by power calculations outlined in the fMRI study protocol and MOP. To achieve this, we estimate having to enroll up to 60 eligible study participants into the fMRI study.

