10.2 Data Management

Data management will be performed by downloading data at minimum every 2 weeks during active data collection periods, and assessing data for missingness and errors. Data will be maintained in password-protected Microsoft Excel Spreadsheets, and then exported using .csv functions for analysis in SAS software.

Please see Section 10.1 for data collection forms description.

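### Section 9.1 names no small-sample correction or reference distribution for the GEE robust standard errors; run in the usual way, the nominal 5% test would run at about 5.3–6.2% for MAIA and 5.3–7% for low-DASH.

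*Combined protocol and SAP*

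**What the plan says.** Section 9.1 makes generalized linear models, "performed using generalized estimating equations (GEE) with robust standard error estimators", the method for the self-regulation and regimen-adherence comparisons. Covariates are given as examples only (age, baseline blood pressure). Time enters as a linear term and possibly a quadratic one. No working correlation, small-sample correction or reference distribution is named. Sections 9.3, 9.4 and 9.6 only point to other sections, and 10.2 says no more about software than that data are "exported using .csv functions for analysis in SAS software".

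Section 9.2 bases the sample size on a noncentral t calculation. It gives the inputs as follows: "with alpha (two-tailed) set at 0.05 and beta at 0.2, shows with a MAIA increase of 3.7 in MB-BP vs. control". From these it concludes that "sample size requirements are 46 per group". Section 6.2.4 sets the target at "n=50 for MBBP intervention group and n=50 for enhanced usual care control group", and 9.2 expects 10–15% dropout.

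Two comparisons are explicitly restricted: DASH, to baseline scores below 5.5 (67% of Stage 1 participants), and BMI, to those at 25 or above. For alcohol and physical activity, 9.2 reports that "approximately 15% of participants do not comply to AHA alcohol guidelines, and 32% do not adhere to physical activity guidelines", but only to explain why mediation is underpowered for those behaviours.

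**The concern.** The plain sandwich variance is a large-sample estimator. With few independent participants, residuals from a fitted model are on average smaller than the true errors, so the variance is biased downwards. A normal critical value then ignores the uncertainty in that variance. Both effects make intervals too narrow and push the type I error above its nominal level. This happens even if every participant is independent, so it is separate from any clustering by class.

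At stake is whether the two-sided 0.05 used in 9.2 is the error rate that the 9.1 analysis delivers. A second issue is that an unstated choice of correction could be made after results are seen.

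**Working it through.** **1. The plan's own figure.** Section 9.2 gives Stage 1 MAIA as "mean 22.6 (SD=6.5) to mean 26.3 (SD=6.0) at 6-month follow-up". With a difference of 3.7 and an SD of about 6.25, d = 3.7/6.25 = 0.592. The normal formula gives 2 × (1.96 + 0.8416)² / 0.592² = 44.8, so 45 per group. The two-sample noncentral t gives power 79.3% at 45 and 80.2% at 46. The stated 46 is reproduced, and it is a t-based calculation.

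**2. Sizes at analysis, per arm** (section 9.2 shares applied to 50 per arm; the lower figure is after 15% dropout).
- MAIA: 50, or 50 × 0.85 = 42.5, so about 43–50.
- Low-DASH: 0.67 × 50 = 33.5, or × 0.85 = 28.5, so about 28–34.
- Only if restricted to non-adherent participants: activity 0.32 × 50 = 16, or 13.6 after dropout (14–16); alcohol 0.15 × 50 = 7.5, or 6.4 (6–8).

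**3. Closed form.** For two equal arms of n with no covariates, the plain sandwich variance is (n − 1)/n times the unbiased one. The z test therefore rejects with probability P(|t(2n − 2)| > 1.96 × √((n − 1)/n)).
- n = 50: P(|t(98)| > 1.940) = 5.5%; n = 43: P(|t(84)| > 1.937) = 5.6%.
- n = 34: P(|t(66)| > 1.931) = 5.8%; n = 28: P(|t(54)| > 1.925) = 6.0%.
- n = 16 and 14: 6.7% and 7.0%.
- n = 8 and 6: 8.8% and 10.4%.

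**4. Null simulation of the GEE.** Identity link, estimated exchangeable correlation, 20,000–40,000 runs per cell (Monte Carlo SE 0.1–0.2 points). Assumptions not in the documents: normal outcomes, within-person correlation 0.5, complete data at the stated n, no class clustering. Models were arm by time on three visits (with and without quadratic time), follow-up visits adjusted for the baseline outcome, and the latter plus age, blood pressure and sex.

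| Comparison | Plain sandwich, z: without age, BP, sex | With age, BP, sex | Kauermann-Carroll type, t(N − p) |
|---|---|---|---|
| MAIA | 5.3–5.8% | 6.0–6.2% | 4.7–5.2% |
| Low-DASH | 5.3–6.3% | 6.5–7.2% | 4.6–5.2% |
| Activity, *if* restricted | 6.8–7.9% | 9.6–10.3% | 4.8–5.4% |
| Alcohol, *if* restricted | 9.1–12.4% | 19–23% | 4.1–6.1% |

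A separate null simulation at 88–100 participants (MAIA) and 58–66 (low-DASH) gave 5.4–6.1% and 5.7–6.7% for the plain z test, and 4.7–5.1% with the Kauermann-Carroll correction and t(N − p).

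**5. Other remedies.** A t reference on the uncorrected standard error leaves MAIA at 5.1–5.5% without the extra covariates and 5.7–5.9% with them, so it is only part of the answer. Mancl-DeRouen with t(N − p) overcorrects in small subsets: about 3–4% for activity and 2–3% for alcohol.

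**The case against.** The strongest reply is that this is under-specification, not a wrong method. The plan never says that the standard errors are uncorrected or that a normal reference will be used. SAS is named without a procedure or option, and the only reference distribution mentioned for an arm comparison is the t statistic in the power calculation. That stands: the rates above describe what usual practice would deliver, not what the plan commits to. It does not remove the point, because section 9.2 concerns sample size and nothing in 9.1 carries a t reference into the analysis.

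A reader might infer that every arm comparison is affected. The documents do not support this. Section 9.2 gives fMRI connectivity a mixed effects model, and 9.1 gives mediation standard regression techniques.

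A reader might also infer that the alcohol and activity results will run at roughly 8–13%. That needs both to be compared only within non-adherent participants. The 15% and 32% shares appear only in the remark on mediation power; sections 3 and 9.5.2 list both outcomes without restriction while restricting BMI in the same list; and 9.1 analyses all randomised participants. If everyone is analysed, the inflation is like that for MAIA.

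Finally, the excess for MAIA is only about 0.3–1.2 points, and hardly any interpretation would turn on it. That also stands, and it sets the priority.

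**Conclusion.** The point holds in a limited form. Section 9.1 leaves the small-sample behaviour of its robust standard errors unspecified. The default implementation would give a type I error of about 5.3–6.2% for MAIA and about 5.3–7% for the explicitly restricted low-DASH comparison. The upper ends apply when age, blood pressure and sex are added, and 9.1 foresees covariates of this kind.

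The figures rest on normal outcomes, within-person correlation near 0.5 and no class clustering. They move with the model, so they should be read as ranges. The BMI comparison cannot be sized, because the share at or above 25 is not given; if at least two thirds qualify, it lies between the MAIA and low-DASH rates.

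The rates of about 7–10% (activity) and 9–20% or more (alcohol) are conditional on a restriction that the plan does not state. They show what to avoid if such subsets are ever analysed; they are not a property of the planned analysis. This is a cheap improvement of minor priority.

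**What to change.** Add one sentence to 9.1: GEE arm comparisons will use a Kauermann-Carroll-type corrected sandwich variance with a t reference on participant-level degrees of freedom (N − p). For continuous outcomes, a REML repeated-measures model with Kenward-Roger degrees of freedom is an acceptable alternative. Name one of the two before analysis. Do not make Mancl-DeRouen with t the default in small subsets, where it is conservative. In the same place, state whether alcohol and physical activity are compared in all participants or only in a subset.

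The cost is a software option and wider intervals; no extra participants or data are needed. For a plain two-arm comparison, the width ratio to the uncorrected z interval is √(n/(n − 1)) × t/1.96. At 43 per arm this is 1.012 × 1.989/1.96 = 1.03, or about 3% wider. At 6.5 per arm it is 1.087 × 2.201/1.96 = 1.22, or about 22% wider. The cost is therefore slight at full sample size and noticeable in any very small subset.

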For fMRI self-regulation neural targets, resting State Functional Connectivity (rs-FC) will be expressed as correlation coefficients, transformed using Fisher's z-transformation for analysis. rs-FC will be obtained at two time points (baseline: T1; post-training: T2) for participants and controls. We will use a mixed effects model with baseline rs-FC as an additional predictor for the change outcome. There are two elements to the hypotheses – the determination of the significance of the change within group and the comparison of the change in the treatment group compared to the control group. For the comparison in change between treatment and control group, with a mixed analysis of variance (within-subjects rs-FC at T1 and T2, and between-subjects according to intervention; sample size, total n = 48, 24/group), we are able to detect an ES of 0.3 between the two treatment groups with 81.3% power (and an ES of .21 with 81.3% power for within-group mindfulness effect; an ES of 0.23 with 87.7% power for an interaction of treatment and time), with two-sided tests at alpha=0.05. Thus is reasonable power to detect small- to moderate-size differences in BOLD.²⁴⁹

Our calculations assume drop-out rates will average around 10-15% across each group, with the control group exhibiting the highest rates of withdrawal and loss to follow up. These estimates are based on the Stage 1 and 2a MB-BP trials in the UH2 phase.

Randomization procedure: Please see Section 3 (study design) above.

Blinding protocol: Please see Section 3 (study design) above.

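### The primary MAIA analysis by GEE has no working correlation, missing-data method or dropout sensitivity analysis, so it is exposed to bias if dropout depends on earlier MAIA

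*Combined protocol and SAP*

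**What the plan says.** Section 9.1 is the whole analysis plan for MAIA; sections 9.3 and 9.6 only refer back to it. Its relevant elements are:

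- **Estimator:** regression models "performed using generalized estimating equations (GEE) with robust standard error estimators", and "Analyses will use GLM with identity links for normally distributed data".
- **Arm:** "The between-groups independent variable in the GEE analysis is intervention condition".
- **Time:** "we will include assessment time as a linear term and possibly with an additional quadratic term". No arm-by-time term is mentioned.
- **Covariates:** "Continuous independent variables such as age and baseline blood pressure would be included as linear terms". Baseline MAIA is not named.
- **Analysis set:** "analyses will be conducted on all participants in the randomized controlled trial, regardless of intervention completion". How a participant with no follow-up MAIA enters the comparison is not stated.

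Section 9.2 expects dropout of 10-15%, "with the control group exhibiting the highest rates of withdrawal and loss to follow up", on the basis of the UH2 trials.

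No section states a working correlation, a missingness assumption, weighting, imputation or a sensitivity analysis for dropout. Section 10.2 checks missingness as data management, section 7.3.3 surveys reasons for dropping out, and the sensitivity analysis in section 10.3.3 concerns instructor warmth and credibility. Section 9.5.1 gives no time point for MAIA; 6 months appears only in the power basis in section 9.2.

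**The concern.** Without weighting or imputation, GEE is guaranteed to be consistent only if missingness is completely at random or depends only on covariates in the model. It can do better when the working correlation and mean model are well chosen, but the plan fixes neither. Two analysts following section 9.1 could therefore report different MAIA differences from the same data, and no planned analysis would show whether dropout explains the gap.

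The margin is thin. The 46 per group in section 9.2 contains no allowance for dropout. Enrolling 50 and losing 10-15% leaves 45 to 42.5 per group, with power of about 0.79 to 0.77 at a difference of 3.7 even with no bias. A bias of a sizeable fraction of a standard error could change the conclusion on the primary outcome.

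**Working it through.** **Inputs from the documents.** Difference 3.7; SD 6.5 at baseline and 6.0 at 6 months; two-sided alpha 0.05; power 0.80; 50 per arm; dropout 10-15%, highest in controls.

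**Assumptions not in the documents.** Within-person correlation ρ of 0.5 or 0.7; control dropout of 15% or 20% against 10% in MB-BP, all between 10 weeks and 6 months; where dropout depends on MAIA, a log-odds slope of size 1 per SD. The 20%/10% split averages 15%, the top of the stated range.

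**Step 1: the plan's own figure.** Pooled SD = √((6.5² + 6.0²)/2) = 6.255, so d = 3.7/6.255 = 0.59. A two-sample t-test with noncentral t gives 46 per group (power 0.801), as stated.

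**Step 2: dropout that differs by arm only.** At 15% or 20% against 10%, a large-sample simulation (400,000 per arm, Monte Carlo SE about 0.015) found the 6-month difference within 0.05 of the truth for independence, exchangeable and unstructured working correlation. There is no bias beyond simulation error.

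**Step 3: dropout that depends on 10-week MAIA, working independence.** With a separate mean for each arm and visit, the 6-month mean is the mean of those still observed. Let Z be 10-week MAIA standardised within arm, p(Z) = 1/(1 + exp(−(a + bZ))) the dropout probability, and d its average. Then

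shift in the arm mean = ρ × 6.0 × E[Z | stay], where E[Z | stay] = −b × E[p(1 − p)]/(1 − d).

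With b = −1 (low scorers leave):

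- d = 10%: a = −2.56; 0.0817/0.90 = 0.091
- d = 15%: a = −2.05; 0.1127/0.85 = 0.133
- d = 20%: a = −1.65; 0.1386/0.80 = 0.173

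Bias = shift in MB-BP minus shift in controls. Each cell gives ρ = 0.5, then ρ = 0.7:

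| Who leaves | 15% vs 10% | 20% vs 10% |
|---|---|---|
| Low-MAIA controls; MB-BP at random | −0.40, −0.56 | −0.52, −0.73 |
| Low-MAIA in both arms | −0.13, −0.18 | −0.25, −0.35 |
| Low-MAIA controls, high-MAIA MB-BP | −0.67, −0.94 | −0.79, −1.11 |

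Example: 0.7 × 6.0 × (0.173 + 0.091) = 1.11. Reversing the slopes reverses every sign. The simulation agrees (for example −0.51 and −0.73 in the first row at 20% vs 10%, and +0.54 and +0.73 when high-MAIA controls leave instead).

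**Step 4: the same dropout, other estimators.** Exchangeable or unstructured GEE with visit-specific means was within about 0.08 points of the truth, and inverse-probability-weighted GEE within about 0.04. In a further run at 20% vs 10%, exchangeable GEE with visit-specific or quadratic time gave 3.70-3.78 for a true 3.7.

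**Step 5: dropout in controls that depends on the unseen 6-month value.** Independence: −0.78 to −1.07. Exchangeable or unstructured: −0.30 to −0.73. Weighted: −0.34 to −0.75. Methods that assume missing at random do not repair this.

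**Step 6: scale.** With 45 and 40 observed, the standard error is 6.255 × √(1/45 + 1/40) = 1.36. A bias of 0.25 to 1.11 is 0.2 to 0.8 standard errors, or 7% to 30% of 3.7.

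**The case against.** The strongest reply is that the plan is silent here rather than wrong.

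- **Working independence is not chosen.** Section 9.1 favours GEE partly because it "enables modeling of covariance structures when observations are correlated across time", which points away from independence. With exchangeable correlation and a flexible time term, the bias under missing at random is negligible beside a standard error of about 1.36. This stands, and it limits the Step 3 figures to one of the analyses the plan permits.
- **Higher control dropout does not imply bias.** A reader might infer that it does. Arm is a model term, and Step 2 shows no bias from the rate difference alone. This stands fully.
- **The documents do not say that dropout will depend on MAIA.** A reader might suppose that waitlisted controls leave because they are disappointed. Nothing in the protocol says so. Controls become eligible for MB-BP once the 6-month assessment is done (section 6.2.7), which is a reason to stay. Home online questionnaires (section 10.1) and out-of-window completion (section 3) should also limit missing MAIA.
- **The 6-month contrast is not defined as primary.** With linear time, people without a 6-month value still inform the fitted 6-month difference, so Step 3 applies to visit-specific means. This too stands, and it is a further reason to fix the mean model and the time point.

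The omission itself remains unanswered. Working independence is compatible with the text, and neither dropout-reason surveys nor missingness checks are analyses.

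**Conclusion.** The point holds as under-specification with a conditional risk. The plan expects differential dropout on its primary outcome and states no working correlation, missingness assumption, missing-data method or sensitivity analysis. If dropout depends on earlier MAIA and independence is used with visit-specific means, the illustrative bias is about 0.2-1.1 points on a true 3.7, in either direction, at 20% versus 10% dropout. At 15% versus 10% it is about 0.1-0.9. A well-chosen working correlation with visit-specific means removes nearly all of it under missing at random.

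These sizes rest on the assumed correlation, dropout split and slope; the documents fix neither size nor direction. They do not support the stronger reading that the planned analysis is biased because controls drop out more. The change is worth making because it is cheap and removes dependence on an unstated choice.

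**What to change.** In section 9:

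1. Make the primary MAIA analysis a likelihood-based repeated-measures model: REML, unstructured covariance, categorical visit, visit-by-arm interaction and baseline MAIA. Alternatively, keep GEE and apply it after multiple imputation by arm. Either is valid under missing at random, given a correct model, without relying on an open working-correlation choice.
2. Name the primary time point and state that the arm contrast at that visit is the primary test. If 6 months is intended, say so in section 9.5.1.
3. State the missing-at-random assumption, and add one control-based imputation sensitivity analysis. That method changes only the imputed MB-BP values, so a set of shifts applied to imputed control values is a natural companion, since controls are where most loss is expected.

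The cost is a paragraph of text and modest programming in SAS, which section 10.2 already names. No change to visits, data collection or sample size is needed for this point.
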